6.19.6.4. Endoscopy Data Availability

The counts and percentages of available endoscopy data from both Central reader and Investigator interpretation will be summarized at each visit (Baseline, Week 8, Week 32, and End of Study/ET).

6.20. Safety Analysis

All summaries of Safety data will use the Safety population. All data collected during the IP, MP and OLP will be summarized by treatment group. Statistical hypothesis testing will not be performed on any safety results.

6.20.1. Adverse Events

For presentation, adverse event verbatim text will be coded into MedDRA System Organ Class (SOC) and preferred term. For all AE summaries, if a patient has more than one AE within a preferred term, the patient is counted once in that preferred term at the maximum severity and closest relationship to study material or dosing procedure. If a patient has more than one AE within a system organ class, the patient is similarly counted once in that system organ class.

All AE safety summaries by treatment group will separately summarize the incidence of events in the placebo group, each RPC1063 dose group, and RPC1063 dose groups combined.

An overview of AEs will be tabulated by treatment group. The number and percentage of patients in each treatment group will be summarized for the following categories:

- any treatment-emergent AEs
- any SAEs
- treatment-related AEs
- •treatment-related SAEs
- •mild, moderate and severe AEs
- AEs with a start date during IP
- AEs with a start date during MP
- AEs with a start date during OLP
- AEs leading to study discontinuation
- AEs leading to study drug discontinuation

The following AE tables refer to AEs that are reported at any time during the study. The number and percentage of unique patients reporting each treatment-emergent AEs will be summarized by SOC, preferred term, and treatment group. A similar table will also be prepared separately for SAEs. Further, the number of treatment-emergent AEs and SAEs, categorized by SOC, preferred term, maximum severity (mild, moderate, or severe), and treatment group will be summarized. In addition, the number of treatment-emergent AEs and SAEs, categorized by system organ class, preferred term, relationship to study drug, and treatment group will be summarized. Finally, the incidence of AEs by preferred term only will be summarized, sorted by descending frequency in the combined RPC1063 group. All AE tables with both SOC and preferred term will be sorted by SOC alphabetically and then by preferred term in descending AE frequency in the combined RPC1063 treatment group. All of these AE and SAE tables will also be repeated for AEs that are reported with start dates during the IP, during the MP, and during the OLP.

AEs with start dates during a follow-up period will be categorized with the previous study phase.

For AE and SAE tables summarizing maximum severity, patients reporting an event more than once with varying severity will be counted only once with the maximum severity within each system organ class/preferred term. For AE and SAE tables summarizing AEs by drug relationship patients will be counted only once, in the category of the strongest relationship to study drug within each system organ class/preferred term.

AEs of special interest will also be summarized by treatment group. The MedDRA SOC and preferred terms that refer to these AEs will be identified by the clinical study team and the project statistician prior to study unblinding and database lock. Treatment-emergent AEs of special interest are defined as AEs related to the following abnormalities:

- Infections
- Bradycardia and heart conduction abnormalities.
- Pulmonary toxicity as measured by the following Pulmonary Function Test (PFT) parameters: FEV₁, FVC, and DLCO.
- Hepatotoxicity which will be assessed by clinical blood chemistry liver function tests.
- Macular edema
- Cutaneous malignancy.

Complete listings of all AEs will be provided. For each AE, the corresponding severity, relationship to study drug, seriousness (yes/no), and available start and stop dates of the event will be specified.

In addition, data listings of all SAEs, AEs leading to discontinuation, and a listings of deaths will also be provided, displaying details of the death captured on the eCRF. Serious adverse event narratives will be provided for the CSR.

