5.3. Safety Definitions

AE or SAE Onset Date

AE and SAE onset or start dates are reported in the AE eCRFs.

AE or SAE End Date

AE and SAE end dates are reported in the AE eCRFs.

AEs and SAEs

AEs will be recorded from the time written informed consent is signed through the Follow-up visit (last dose + 30 days).

An AE or SAE will be regarded as treatment-emergent if it has a start date during or after the first study drug administration or if it worsened or if the relationship to study drug changed from unrelated to related after the first study drug administration. UC disease relapse and related symptoms will be monitored as study endpoints, but will not be recorded as AEs unless they meet the definition of an SAE.

All AEs or SAEs meeting these criteria with a start date up to and including 30 days following the last dose of treatment with the study drug will be considered treatment-emergent.

Treatment Related AEs

For summary purposes, all AEs classified by the Investigator on the AE eCRF as "possible", "probable" or "related" will be considered treatment related AEs. If the relationship to study drug is unknown or missing, the AE will be considered to be treatment related.

Duration of AEs

The duration of an AE will be calculated as:

Duration = (AE End Date - AE Onset Date) + 1

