5.4. Other Definitions

Age

Age (in years) will be calculated from the date of birth to the date of informed consent. Age will be reported as an integer.

Study Drug

Study drug refers to RPC1063 0.5 mg, RPC1063 1.0 mg, or Placebo oral capsules as well as the titration doses.

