6.8. Analysis Populations

The following analysis populations will be used in the statistical analysis. Analysis population membership will be determined prior to unblinding.

Intent-to-Treat (ITT) Population: The ITT population will consist of all randomized patients who received at least 1 dose of study treatment, with treatment assignment designated according to randomized treatment. This will be the primary population for the analysis of efficacy endpoints.

Per Protocol (PP) Population: The PP population will consist of the subset of the ITT population, excluding those patients who have had a major protocol violation. Major protocol violations will include all violations that would significantly impact assessment of safety and efficacy of the compound and will be finalized in advance of data lock and primary analyses. Violation of any of the following three inclusion criteria related to UC specific disease activity would exclude a patient from the PP population:

- Must have a confirmed diagnosis of UC by endoscopic and histologic evidence
- Must have a baseline Mayo score of 6-12 inclusive with endoscopic subscore of >=2
- Must have a baseline endoscopy with >= 15 cm involvement

Poor study drug compliance will also exclude the patient from the PP population. Poor study drug compliance is defined as taking less than 80% or more than 120% of study treatment during the entire treatment period.

The patients excluded from the PP population will be fully defined and documented with reasons for exclusion prior to database lock.

Safety Population: The Safety population will consist of all patients receiving any study treatment. All patients in the Safety population will be analyzed according to the highest dose of RPC1063 actually received and not according to the treatment they are randomized to receive, in the event there is a discrepancy.

6.9. **DMC**

An independent DMC will be charged with monitoring accumulating data from the trial, as well as general aspects of trial conduct.

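### Any-time adverse-event tables, unrestricted overview rows and the special-interest summary have no cut-off at first open-label dose, so events on open-label 1 mg count in the placebo and 0.5 mg columns

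*SAP*

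**What the plan says.** SAP 4 lets Week 8 non-responders, patients who relapse in the Maintenance Period (MP) and MP completers, from any arm, enter the OLP. All of them then receive 1 mg after titration.

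**Scope.** SAP 6.20: "All data collected during the IP, MP and OLP will be summarized by treatment group". SAP 6.20.1, on the main tables: "The following AE tables refer to AEs that are reported at any time during the study". At the end of that paragraph: "All of these AE and SAE tables will also be repeated for AEs that are reported with start dates during the IP", and likewise for the MP and OLP. The special-interest events come in a later paragraph: "AEs of special interest will also be summarized by treatment group". No period is given there. Of the ten overview rows, three are tied to a period (IP, MP, OLP). The other seven are not: treatment-emergent, serious, treatment-related, treatment-related serious, by severity, and the two discontinuation rows.

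**Window.** SAP 5.3 opens the treatment-emergent window at first study drug and closes it after the last: events "with a start date up to and including 30 days following the last dose of treatment with the study drug will be considered treatment-emergent". SAP 5.4: "Study drug refers to RPC1063 0.5 mg, RPC1063 1.0 mg, or Placebo oral capsules as well as the titration doses".

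**Grouping.** SAP 6.1 names placebo, 0.5 mg and 1.0 mg as the groups for OLP summaries as well, unless otherwise noted. SAP 6.8 analyses the Safety population by the "highest dose of RPC1063 actually received and not according to the treatment they are randomized to receive, in the event there is a discrepancy". Section 3 of the OLP addendum labels OLP safety cohorts by the treatment received in the parent study.

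**The concern.** Comparing the safety of RPC1063 with placebo over the whole study is a stated secondary objective (SAP 3.1.2). The any-time tables look like the display that answers it. Yet a placebo column that includes months on open-label 1 mg is not a placebo column. Where 1 mg raises the rate of an event, some of the excess is credited to placebo and the arms look more alike than they are.

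The special-interest summary matters most here, because it collects the event classes the SAP singles out for close monitoring, and no by-period version of it is stated. SAP 6.8 adds a second uncertainty. It does not say whether moving to 1 mg in the OLP, as planned, counts as a discrepancy from randomised treatment.

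**Working it through.** The documents give no figure to reproduce. The check is a reading of the text followed by an illustration.

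**Text, step by step**

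1. Study drug (5.4) covers placebo and both RPC1063 doses and is not limited to the blinded periods.
2. The window in 5.3 therefore runs unbroken, for a patient who crosses over, from first blinded dose to 30 days after the last OLP dose.
3. The any-time tables, the seven overview rows and the special-interest summary have no other stop.
4. A placebo column in OLP summaries (6.1) has patients in it only if labels are kept. Addendum Section 3 also keeps them.
5. OLP events of placebo and 0.5 mg patients therefore fall in the placebo and 0.5 mg columns.

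**Illustration of dilution (labels kept)**

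From the documents: 9 weeks of induction, 24 weeks of maintenance, and 20 OLP weeks (the minimum in SAP 4 for the last entrant).

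Assumed: constant event hazard h = 0.005 per week on placebo; rate ratio 2, so 0.010 on 1 mg, titration ignored; Week 8 response r = 30–50% in both arms; responders followed for 9 + 24 = 33 weeks and non-responders for 9; OLP uptake u = 50–90%.

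Incidence in an arm with hazard h is the sum over patient paths of

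share of path × [1 − exp(−(h × core weeks + 0.010 × OLP weeks))].

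Worked case, r = 0.3 and u = 0.9, any-time table:

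- Placebo: responders 15.2% without OLP and 30.6% with; non-responders 4.4% and 21.7%. Total = 0.3 × (0.1 × 0.152 + 0.9 × 0.306) + 0.7 × (0.1 × 0.044 + 0.9 × 0.217) = 22.7%.
- 1 mg: 28.1% and 41.1%; 8.6% and 25.2%. The same sum gives 28.4%.
- Ratio 28.4/22.7 = 1.25.

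| Display | Placebo | 1 mg | Ratio |
|---|---|---|---|
| Any-time, r = 0.3, u = 0.9 | 22.7% | 28.4% | 1.25 |
| Any-time, r = 0.5, u = 0.5 | 18.0% | 25.8% | 1.43 |
| Cut at first OLP dose, r = 0.3 | 7.6% | 14.5% | 1.89 |
| Cut at first OLP dose, r = 0.5 | 9.8% | 18.4% | 1.87 |
| Induction only | 4.4% | 8.6% | 1.96 |

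The share of placebo-column follow-up spent on open-label 1 mg is 20u / (33r + 9(1 − r) + 20u). It is 10/31 = 32% (r = u = 0.5) to 18/34.2 = 53% (r = 0.3, u = 0.9).

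**Sensitivity**

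- SAP 4 says OLP non-responders at 8 weeks should discontinue. If half of entrants leave after 9 OLP weeks (assumed), the any-time ratio is 1.32–1.50 instead of 1.25–1.43.
- With 104 OLP weeks it is 1.05–1.15 if all entrants stay, or 1.12–1.27 if half leave after 9 weeks.
- With hazards of 0.002–0.010 per week, rate ratios of 1.5–3 and 20 OLP weeks with all staying, the any-time ratio is 1.14–1.75, against 1.41–2.87 with the cut-off.

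**The case against.** **Separated data already exist.** The treatment-emergent AE and SAE tables by system organ class and preferred term are repeated for the Induction Period (IP), MP and OLP. Special-interest events are identified by those same terms. A reader might infer that they could be seen in the final report only in mixed columns. The documents do not support that: each term can be read by period, and only the grouped special-interest summary is mixed.

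**The primary analysis is clean.** SAP 6.10 restricts all safety summaries at that cut to induction, so an IP comparison with placebo exists. The addendum also opens OLP treatment-emergent events at first OLP dose. Both stand, but neither ends the any-time outputs of the final report at that dose.

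**SAP 6.8 need not conflict with 6.1.** A reader might infer a contradiction, with every crossover moved to the 1 mg group. The condition at the end of the 6.8 sentence, the placebo column required by 6.1 and addendum Section 3 all point the other way. The different OLP form for laboratory data in 6.20.6 fits 6.1's allowance for exceptions. What remains is an ambiguity about planned OLP dosing.

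**The numbers are illustrative.** This stands too. A constant hazard fits poorly for bradycardia, which protocol 11.5 describes as mainly a first-dose effect in fingolimod studies.

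**Nothing is tested.** "Statistical hypothesis testing will not be performed on any safety results". That lowers the stakes, but descriptive columns labelled by arm are still read as comparisons.

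**Conclusion.** The point holds and is minor. As written, the any-time AE and SAE tables, the unrestricted overview rows and the special-interest summary count events on open-label 1 mg under placebo and 0.5 mg. If 1 mg raises an event rate, the crude contrast with placebo in these outputs is pulled towards no difference: a rate ratio of 2 shows as roughly 1.25–1.5 with 20 OLP weeks, against about 1.9 with a cut-off. The direction follows from kept labels. The size rests wholly on the assumed hazard, response, uptake and OLP stay.

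The lasting gap is in the final report, where the grouped special-interest summary and the unrestricted overview rows have no stated by-period version. SAP 6.8 is ambiguous on planned OLP dosing. The conclusion is limited to visible text: SAP Section 2 and addendum Sections 1 and 2 are largely absent from the copy reviewed.

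**What to change.** - **SAP 6.20.1:** end the by-arm AE, SAE, overview and special-interest comparisons with placebo at first OLP dose, or give them by IP and MP. Add the special-interest summary and all overview rows to the by-period repeats. Report OLP events under 1 mg in an OLP table or an all-RPC1063-exposure table.
- **SAP 6.8:** state that the safety group is the treatment actually received in the IP and MP, and that planned OLP dosing is not a discrepancy.

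The cost is SAP wording and modest table reprogramming. No new data are needed, because the by-period tables already require OLP start dates.

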6.20.2. Physical Examinations

A complete physical examination will include evaluation of heart, lung, head and neck, abdominal, neurological, skin, and extremities. An interim (or brief) physical examination will include areas with previously noted abnormalities and/or that are associated with any new complaints from the patient.

Abnormal physical examination findings at each visit will be listed.

6.20.3. Height and Weight

Height will be measured at screening. Weight will be monitored throughout the study.

6.20.4. Vital Signs

Heart rate (HR) and systolic/diastolic blood pressure (BP) will be assessed at scheduled times as outlined in protocol.

After the patient has been supine for at least 15 minutes, HR and BP will be measured 3 times using an automated validated device. The repeat HR and BP measurements will be made at 2-minute intervals. The lowest predose HR and BP (based on Systolic BP) will be taken as the baseline measure and used as comparison to postdose values. BP will then be measured in the same manner with the patient in the standing position. A sudden, significant fall in BP (> 20 mmHg) between 2 and 5 minutes after standing from the supine position will be interpreted as orthostatic hypotension and will be documented in the patient chart and eCRF.

After the first dose of study treatment, patients will be carefully monitored during a 6-hour post-dose monitoring period of hourly recording of HR (supine) and BP (supine and orthostatic). During the 6-hour post-dose monitoring on Day 1, after the patient has been supine for at least 5 minutes, HR and BP will be measured once using an automated validated device. Any clinically relevant change from baseline should be confirmed on repeat measures. Blood pressure will then be measured in the same manner with the patient in the standing position. The same orthostatic hypotension criteria stated above will be applied.

Heart rate and systolic and diastolic blood pressure will be summarized using descriptive statistics at each timepoint by treatment group. BP measurements will be summarized separately in the supine and orthostatic positions. Any clinically significant changes will be recorded as AEs or SAEs.

For patients participating in cardiac monitoring on Day 5, a summary table will be provided that summarizes the hourly change from pre-dose assessment through hour 6 at each of the baseline and Day 5, visits by treatment group for heart rate and blood pressure.

Box plots will be provided to display the distribution of HR and BP. In addition, line plots will be created to display the change from baseline over the entire study period and change from pre-dose in HR and BP for the baseline and Day 5visits.

The number and percentage of subjects with clinically relevant abnormalities will be presented by treatment group. The criteria for clinically relevant abnormalities are shown in the following table.

Table 1. Criteria to Determine Clinically Relevant Abnormalities in Vital Signs

Vital Sign	Criteria for Abnormalities
Temperature	>38°C and an increase from pre-dosing of at least 1°C
Heart Rate	>120 beats per minute post-baseline, or
	an increase from pre-dosing of more than 20 beats per minute, or
	<45 beats per minute post-baseline, or
	a decrease from pre-dosing of more than 20 beats per minute
Systolic Blood Pressure	>180 mmHg post-baseline, or
	an increase from pre-dosing of more than 40 mmHg, or
	<90 mmHg post-baseline, or
	a decrease from pre-dosing of more than 30 mmHg
Diastolic Blood Pressure	>105 mmHg post-baseline, or
	an increase from pre-dosing of more than 30 mmHg, or
	<50 mmHg post-baseline, or
	a decrease from pre-dosing of more than 30 mmHg

All vital sign measurements will also be listed.

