11.2. Clinical Safety Assessments

Physical Examination

A complete physical examination will include evaluation of heart, lung, head and neck, abdominal, neurological, full examination of the skin for lesions, and extremities. An interim (or brief) physical examination will include areas with previously noted abnormalities and/or that are associated with any new complaints from the patient. In addition, patients will be questioned on visual symptoms (i.e., blurred vision or decreased visual acuity) during both the complete and interim physical examinations.

All significant findings that are present at screening must be reported on the relevant medical history/current medical conditions eCRF. Significant findings made after randomization that meet the definition of an AE must be recorded on the AEs eCRF.

Height and Weight

Height will be measured at screening. Weight will be monitored throughout the study.

Vital Signs

Heart rate and blood pressure (systolic and diastolic) will be assessed per the Schedule of Events (Table 1 and Table 2).

When obtaining the predose HR and BP during dose escalation (Day 1/IOLP), the patient should rest in the supine position for at least 15 minutes before measurement to establish an accurate baseline measurement. After the patient has been supine for at least 15 minutes, HR and BP will be measured 3 times. An automated validated device can be used, if available. In case the cuff sizes available are not large enough for the patient's arm circumference, a sphygmomanometer with an appropriately sized cuff may be used. The repeat HR and BP measurements will be made at 2-minute intervals. The lowest predose value of supine HR and BP (based on the systolic BP) should be taken as the baseline measure and used for comparison to postdose values. Orthostatic blood pressure will then be measured once with the patient in the standing position (after standing for 2 minutes). A sudden, significant fall in BP (> 20 mmHg) between 2 and 5 minutes after standing from the supine position will be interpreted as orthostatic hypotension and will be documented in the patient chart and eCRF.

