5.1. Time Point Definitions

Study Day for Induction and Maintenance Periods

All visit data will be assigned a study day, from the Visit 1 in the Induction Period according to the following rules:

- Visit 1 Day will be designated as Day 1
- All other days after Day 1: Study Day = (Visit Date Visit 1 Date + 1)
- All other days before Day 1: Study Day = (Visit Date Visit 1 Date)

Study days for evaluations occurring during the Screening visit will be negative numbers (e.g., "-7"), no Day 0 is defined for this study.

Study Day for the Open Label Period

All visit data will be assigned a study day, from the Visit 1 in the Open Label Period according to the following rules:

- OLP Day 1 will be designated as Day 1
- All other days after OLP Day 1: Open Label Day = (Visit Date Open Label Visit 1 Date + 1)
- All other days before OLP Day 1: Open Label Day = (Visit Date Open Label Visit 1 Date)

Baseline Measurement

There will be two baseline definitions:

Baseline: The latest assessments completed prior to initial study drug administration will be used as the Baseline measurement for all analyses for the IP and MP. It will also be used as the Baseline measurement for efficacy analyses for the OLP.

Treatment Baseline: The last assessment prior to initial administration of RPC1063 will be used as the Baseline measurement for safety analyses for the OLP.

Visits

Visits identifiers on the study electronic case report forms (eCRFs) will be used.

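### A lowest-of-three predose baseline set against single postdose readings makes each arm's mean fall in heart rate or systolic BP look smaller, by about 0.85 within-session SD if readings are independent

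*SAP*

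**What the plan says.** SAP 6.20.4 describes the predose measurement: "After the patient has been supine for at least 15 minutes, HR and BP will be measured 3 times using an automated validated device", and "The repeat HR and BP measurements will be made at 2-minute intervals". It then sets the baseline: "The lowest predose HR and BP (based on Systolic BP) will be taken as the baseline measure and used as comparison to postdose values". Protocol 11.2 agrees: "The lowest predose value of supine HR and BP (based on the systolic BP) should be taken as the baseline measure".

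During the six hours after the first dose, readings are hourly and single: "after the patient has been supine for at least 5 minutes, HR and BP will be measured once using an automated validated device". A clinically relevant change is to be confirmed by repeat measurement.

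Three outputs in SAP 6.20.4 use a change:
- a table of hourly change from predose to hour 6, at the baseline and Day 5 visits, for patients with Day 5 cardiac monitoring;
- line plots of change from baseline over the whole study, and of change from predose at those two visits;
- Table 1, which counts patients with clinically relevant abnormalities. For heart rate, one criterion is "a decrease from pre-dosing of more than 20 beats per minute"; another is an absolute value below 45 bpm.

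SAP 5.1 has a general rule: "The latest assessments completed prior to initial study drug administration will be used as the Baseline measurement for all analyses". Table 1 does not say whether *pre-dosing* means the lowest of three or the latest value.

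**The concern.** The two sides of the comparison are not alike. The baseline is picked as the lowest of three noisy readings, while each postdose value is one noisy reading with no selection. Even if nothing happens to a patient, the postdose value is expected to be above the baseline.

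Bradycardia is a special-interest event in this trial, and the first-dose fall in heart rate is the reason for Day 1 monitoring. A reader of the change tables and plots will take the mean change in each arm as the size of that fall. A summary that is shifted toward a smaller fall, and toward an apparent rise on placebo, describes the effect wrongly.

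**Working it through.** **Inputs from the documents.** Three predose supine readings, 2 minutes apart; lowest taken as baseline; one reading at each of six postdose hours; a drop of more than 20 bpm as one Table 1 criterion. The documents give no heart-rate SD, expected fall or expected count, so there is no figure of the plan to reproduce.

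**Assumed.** Within-session SD σ of a single reading: 3 to 6 bpm. Other assumptions are stated where used.

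**1. Shift in the mean change.** For three independent normal readings, the expected minimum lies 3/(2√π) = 0.846 SD below the mean. Hence

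expected (postdose − lowest predose) = true change + 0.846σ.

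| σ (bpm) | 3 | 4 | 5 | 6 |
|---|---|---|---|---|
| Shift (bpm) | 2.5 | 3.4 | 4.2 | 5.1 |

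With σ = 4, a true mean fall of 10 bpm appears as 10 − 3.4 = 6.6 bpm, and an arm with no effect shows a rise of 3.4 bpm.

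**2. Correlated readings.** Readings 2 minutes apart may share part of their noise. If half the noise variance is shared, the shift is 0.846 × √0.5 × σ = 0.60σ, or 1.8 to 3.6 bpm for σ of 3 to 6.

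**3. The other reading of the rule.** The words on systolic BP may mean that heart rate is taken from the reading with the lowest systolic value. Systolic BP then carries the full 0.85 SD (of its own within-session SD). The heart-rate shift becomes r × 0.846σ, where r is the within-session correlation of the two. For an assumed r of 0 to 0.4 this is 0 to 0.34σ, at most 1.0 bpm (σ = 3) to 2.0 bpm (σ = 6).

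**4. Difference between arms.** The predose readings precede the drug, so the same 0.846σ is added in every arm and cancels: (Δ_active + 0.846σ) − (Δ_placebo + 0.846σ) = Δ_active − Δ_placebo.

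**5. Count of drops above 20 bpm.** Assume a true mean drop of 10 bpm with between-patient SD 6. The noise-free share above 20 is P(Z > 10/6) = 4.8%.

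- *One postdose reading, mean baseline:* the variance is 36 + σ² + σ²/3. For σ = 3, P(Z > 10/√48) = 7.4%; for σ = 6, P(Z > 10/√84) = 13.8%.
- *One postdose reading, lowest baseline:* the mean drop falls by 0.846σ, and the minimum has variance 0.56σ². For σ = 3, P(Z > (20 − 7.46)/7.07) = 3.8%; for σ = 6, P(Z > (20 − 4.92)/9.60) = 5.8%. Simulation agrees.
- *Any of six hourly readings* (simulated, assumed hourly profile 0.3, 0.5, 0.7, 0.9, 1.0, 0.9 of the full drop): lowest baseline 5.2% and 11.5%, mean baseline about 10% and 27%, for σ = 3 and 6.

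Here the lowest baseline is nearer the true share. Other inputs reverse this: with mean drop 15, between-patient SD 8, σ = 4 and one reading at the nadir hour, the lowest baseline gives 18.7% and the mean baseline 29.4%, against a true P(Z > 5/8) = 26.6%.

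Over 80 simulated any-of-six scenarios (σ 2 to 6, mean drop 5 to 20, between-patient SD 5 or 8, none or half of the predose noise variance shared), the count under the lowest baseline was 0.30 to 0.89 of that under the mean baseline, median 0.64. For mean drops of 10 to 15 bpm, the ratio to the true share was 0.85 to 6.8 (median 1.2) with the lowest baseline and 1.1 to 12 (median 1.9) with the mean.

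**The case against.** The strongest objection concerns the threshold count. A reader might infer that the rule roughly halves the number of patients with a drop above 20 bpm on active drug, and so hides bradycardia. The documents do not support that. They give none of the three quantities that fix the ratio, and a ratio to the mean-baseline count is not a ratio to the truth. When any of six noisy postdose readings can qualify, taking the lowest of those pushes the count up and offsets the low baseline. Moving Table 1 wholly to the mean could make that count worse. This objection stands, and the point below is limited accordingly.

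Other safeguards exist. Heart rate below 45 bpm needs no baseline, a 24-hour Holter and a 6-hour ECG are done on Day 1, relevant changes are confirmed by repeat measurement (not modelled here), special-interest events are summarised from adverse event terms, all vital signs are listed, and no safety tests are planned. All of this limits the harm. None of it corrects the mean changes in the tables and plots.

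The shift is equal in all arms. That protects the difference between arms, but the planned outputs are summaries by arm.

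The rule is also in the protocol, so a change to the SAP is a departure that must be recorded. A conflict with SAP 5.1 might be inferred too, but the specific rule in 6.20.4 can be read as overriding the general one. What remains is that Table 1 leaves its own reference undefined.

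**Conclusion.** The concern holds for the within-arm mean changes. With independent readings, each hourly mean change is shifted upward by about 0.85 within-session SD: 2.5 to 5.1 bpm in heart rate for an assumed SD of 3 to 6 bpm, and less if the three readings are correlated. If heart rate is taken from the lowest-systolic reading, the heart-rate shift is small and the full shift falls on systolic BP. The direction follows from the rule itself; the size in bpm rests on an SD that the documents do not give.

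Differences between arms in mean change are unbiased. For the count of drops above 20 bpm, neither size nor direction of error against the true share is established, so a claim that the count is halved, or that the table is anti-conservative, goes beyond the documents.

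**What to change.** In SAP 6.20.4:

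1. Use the mean of the three predose readings as baseline for the Day 1 hourly change summaries and the change line plots. Keep the lowest-reading version as a supplement.
2. Record this as a departure from protocol 11.2 in SAP section 8.
3. State which baseline *pre-dosing* means in Table 1, and show the relative-change counts there under both baselines.
4. State, for the supplement, whether heart rate is the lowest of its own three values or the value paired with the lowest systolic BP.

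Leave the sites' Day 1 use of the lowest reading unchanged.

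The cost is SAP wording and one extra derivation, which needs all three readings in the database. Within-arm heart-rate changes will look slightly less favourable.
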